2.3.2 Fitting Software (FS)

Two different fitting software platforms will be used for fitting of sound processors during this clinical investigation, the Baha Fitting Software (BFS) (currently released version) for the reference device Baha Power Sound Processor, and the Osia™ Fitting Software (OFS) CSDS Clin Trial version 1.02 for evaluation of the ATB Sound Processor.

The investigator shall use the BFS to configure the Baha BP110 Power Sound Processor for each subject/user at visit 1. Communication between the fitting software and the sound processor shall be achieved using a Hi-Pro 2 programming interface from GN Otometrics (GNO) and a Programming Cable Long Blue/Red (Figure 6).

The investigator shall use the OFS to configure the operational features of the Osia Sound Processor for each subject/user at visit 4. Communication between the fitting software and the sound processor is achieved using a Freedom Programming Pod, Cochlear Nucleus Programming Shoe with Cable as well as CP950 Programming Shoe Adaptor Cable Kit and two Battery ZN Air P675 Implant Plus.

This fitting software for the Osia Sound Processor version 1.02 is built on and has equivalent graphical user interface and features as the current regulatory approved Baha Fitting Software (BFS). Complete information is found in the Instruction For Use (IFU) ^{7, 8}.

[figure not shown]

Figure 6. Programming set-up for a BP110, Hi-Pro2 and computer

2.3.3 Programming pod

The Freedom Programming Pod, approved and used for Cochlear's CI products, will be used as it is with the ATB System. The programming pod provides a connection between the programming computer and the ATB Sound Processor via a USB cable and a programming shoe with cable as well as an adaptor cable kit and two batteries.

2.3.4 Intraoperative test system

An intraoperative test system Osia™ Intraoperative Test System (IOTS) CSDS Clin Trial version 1.01 will be available to confirm device integrity at the time of implantation. An intraoperative test system is available and in use for Cochlear Implants and Codacs to verify the functionality. For ATB System, the IOTS will evaluate any potential damages to the piezo-element and to the lead before surgical closure. The integrity test will be a mandatory step of the surgical procedure, and will be performed just before the actuator is mounted onto the BI300 Implant. The IOTS functions by measuring the CBAS5539 CIP Version 5

current consumed by the implant's audio circuitry (including the actuator). The measured frequency response provides an indication of the state of the actuator and of the actuator lead.

The test system concept is similar to the existing intraoperative tests available for CI and Codacs, and uses a number of similar and/or identical components (including a computer with dedicated software, Osia Sound Processor, Freedom Programming Pod, Cochlear Nucleus Programming Shoe with Cable as well as CP950 Programming Shoe Adaptor Cable Kit and two Battery ZN Air P675 Implant Plus (Figure 7). The test also relies on the use of a custom silicone Isolator to provide mechanical isolation for the actuator during the test (Figure 8). The Isolator will come pre-mounted on the actuator inside the sterile blister packaging. During the test the receiver-stimulator will already be in place under the patient's skin and the actuator will be mounted in the Isolator (which is secured to the BI300 Implant using the Guide pin). The test takes approximately two minutes to perform, and the software provides the user with an unambiguous test result regarding device integrity prior to closing and suturing the surgical site. A Signal Check wand (currently available for CI and Codacs) is also available to check the radio-frequency (RF) link between the transmitting coil of the sound processor and the internal coil in case of no response from the implant is received during the intraoperative test. The sound processor should be switched on and the Signal Check wand held to the coil. If the signal check lights up the coil is working.

1. Adapter cable
2. Battery retention clip
3. Clothing clip

Figure 7. Intraoperative Test System (IOTS) concept

Figure 8. ATB Implant, with actuator pre-mounted onto the Isolator.

2.3.5 Reference device

The ATB System will provide similar output and audiological performance as the Cochlear Baha BP110 Power Sound Processor. The BP110 Power Sound Process will be used as reference device in this clinical investigation. The BP110 Sound Processor on a Softband will be used at the first visit for the subject, before the surgery visit, to measure preoperative Sound Processor performance and to prepare the subject for the postoperative hearing situation. The BP110 Sound Processor is a fully programmable, head-worn sound processor, with automatic signal processing, which is regulatory approved for use together with Baha systems (Baha Connect and Baha Attract) and together with a Baha Softband (Figure 9). This sound processor is secured to the Baha Softband by means of a snap coupling. The sound processor has several automatic systems, including active feedback cancellation through phase cancellation, automatic adaptive multi-band directional microphones, wide dynamic range compression and automatic noise management. The transducer is driven by a size 675 battery.

Figure 9. Cochlear Baha BP110 Power Sound Processor and Baha Softband

All other non-investigational devices, are listed in Appendix 2.

2.3.5.1 Manufacturer of the non-investigational devices

| | |
|--|--|
| 
Cochlear Limited, Sydney, Australia
 | 
 • ATB specific Reusable Instruments • ATB specific Single Use Instruments • Cochlear Nucleus Reusable Instruments • Osia™ Fitting Software CSDS Clin Trial version 1.02 • Freedom Programming Pod • Osia™ Intraoperative Test Software CSDS |
|--|--|

CBAS5539 CIP Version 5

| | |
|-------------------------------------|--|
| | 
Clin Trial version 1.01
 
 • Cochlear Nucleus Programming Shoe with Cable CP950 Programming Shoe Adaptor Cable Kit Battery ZN Air P675 Implant Plus • Signal Check (Wand) |
| Cochlear Bone Anchored Solutions AB | 
 • Cochlear Baha Reusable Instruments • Cochlear Baha Single Use Instruments • Baha BP110 Power Sound Processor • Baha Fitting Software (currently released version) • Baha Softband (Unilateral) |

2.4 Treatment after the completion of the investigation

After the clinical investigation the subjects will be able to continue with their investigational device (ATB System). Routine controls with audiological checks will follow local routines according to the standard treatment program for similar devices (e.g. active, non-skin penetrating, bone-conduction hearing devices).

The ATB Implant is expected to have a lifetime of at least 10 years. Any changes to the ATB Implant during or after this time-period should be performed according to the ATB Implant revision/replacement procedure described in the professional guide ⁵.

After this clinical investigation, it will be possible to use future upgrades of the ATB Sound Processor, used together with the ATB Implant.

3 SUBJECTS AND SUBJECT PROTECTION

3.1 Selection of subjects

3.1.1 Inclusion criteria

A subject will be eligible for inclusion in the investigation if he/she meets **all** of the criteria below:

- Adult subjects (18 years or older)
- Subject with conductive or mixed hearing loss in the ear to be implanted. Bone conduction thresholds with pure tone average (PTA4; mean of 0.5, 1, 2 and 4 kHz) of ≤ 55 dB HL.

OR

Subject with single-sided sensorineural deafness who is a candidate for Baha surgery. Air conduction thresholds with a pure tone average PTA4 of ≤ 20 dB HL (mean of 0.5, 1, 2 and 3 kHz) in the good ear OR subject who is indicated for an AC CROS but—for some reason—cannot or will not use an AC CROS (Air Conduction-Contralateral Routing of Signal).

- Signed informed consent
- Previous experience from amplified sound through properly fitted amplification. (For example but not limited to Hearing aid, CROS device, Bone conduction hearing device on headband/softband).

3.1.2 Exclusion criteria

A subject will be excluded from participation in the investigation if he/she meets **any** of the criteria below:

- Uncontrolled diabetes as judged by the investigator.
- Condition that could jeopardise osseointegration and/or wound healing (e.g. osteoporosis, psoriasis, long-term systemic use of corticosteroids) or condition that may have an impact on the outcome of the investigation as judged by the investigator.
- Insufficient bone quality and quantity for implantation of a BI300 Implant.
- Subject that has received radiotherapy in the area of implantation, or is planned for such radiotherapy during the study period
- Use of ototoxic drugs that could be harmful to the hearing, as judged by the investigator
- Unable to follow investigational procedures, e.g. to complete quality of life scales.
- Participation in another clinical investigation with pharmaceutical and/or device.
- The subject is pregnant or lactating
- The subject suffers from psychiatric and/or psychosomatic disorder(s).

3.2 Number of subjects

Fifty (50) evaluable subjects (visit 2 performed successfully) will be recruited at five international clinics in order to meet the requirement for recruitment in the investigation. The number of subjects to be included for each centre will be approximately 10. The sponsor will be able to control the inclusion by distribution of devices to each centre.

CBAS5539 CIP Version 5

3.3 Duration of subject participation

Subjects will participate during a 12-month period in total.

3.4 Subject enrolment and Informed consent

Before a subject is asked to sign an informed consent form, an investigator must explain the following to the potential investigational subject:

- The rationale, aims and objectives of the investigation
- Risks and benefits
- Alternative treatments
- Extent of the subject's involvement
- That the subject can withdraw his/her consent at any time
- That the confidentiality of patient data will be maintained at all time
- That the subject will be informed if new information becomes available that may be relevant to the subject's willingness to continue participation in the trial

The subject must have the opportunity to ask any questions. Signed and dated informed consent from potential subjects must be obtained before any investigational procedure can be performed. The investigator will, after informed consent has been obtained, assign a consecutive enrolment number to the subject according to given instructions, e.g. centre 1, subject 101, 102, 103 etc. Centre 2, subject 201, 202, 203 etc.

3.5 Randomisation

This is an open study with no comparator device. Randomisation is not possible.

3.6 Discontinuation

- Subjects are free to discontinue their participation in the investigation at any time
- Subjects may be discontinued from the investigation at any time at the discretion of the investigator
- Other reason for subject withdrawal or discontinuation, e.g. implant loss

Subjects who themselves discontinue from the investigation should always be asked about the reason(s) for the discontinuation and the presence of any adverse events. If possible, the subject should always be seen and assessed by an investigator. Any adverse event should be followed up.

3.7 Replacement of subjects

If a subject discontinues his/her participation in the investigation, he/she will not be replaced if this discontinuation occurs after surgery is performed. If this discontinuation occurs before surgery the subject will be replaced in order to reach 50 evaluable subjects.

3.8 Insurance

In case of any damage or injury occurring during the participation in the investigation, the Sponsor has contracted an insurance company, Willis Australia Limited, which will cover the liability of the Sponsor, the investigators and other persons involved in the investigation. The Sponsor may use a local insurance company, where applicable, according to national legislation.

CBAS5539 CIP Version 5

4 DESIGN OF THE CLINICAL INVESTIGATION

4.1 Design of the clinical investigation

This clinical investigation is an open, two armed, prospective, multicentre clinical investigation and is divided into a 3-month period (primary efficacy analysis) followed by an additional 9 months of follow-up for the complete 12 months period. The primary safety endpoint is 6 months. One arm is selected for conductive and mixed hearing loss subjects, the other arm is selected for single-sided sensorineural deafness subjects. Each subject will be compared to his/her own preoperative unaided hearing situation, with the Baha BP110 Power Sound Processor on a softband preoperatively and with the Investigational device at 3 months. If applicable subjects with a current hearing amplification will also be tested preoperatively.

4.2 Justification for the design of the clinical investigation

The design where the primary assessment consist of a comparison of the post-operative aided performance with the preoperative unaided performance is considered relevant for this purpose. The primary efficacy assessment of the investigation, i.e. threshold, free-field, pure tone average PTA4, is a relevant and objective method used by clinics internationally as a way to assess hearing performance. The test is not language specific (no words used), thus rendering comparative data in an international, multilingual setting.

The self-reported assessment of hearing outcome using the APHAB questionnaire was chosen as an important secondary efficacy assessment; hence, the APHAB scale was used for determination of the sample size in the investigation⁹. The APHAB has been used in investigations previously and has shown to be a good tool for measuring changes in patient benefits.

The rationale for measuring and collect data with Baha BP110 Power Sound Processor on a Softband as a secondary assessment is based on the fact that the FDA guideline for middle ear implants suggests that a comparative non-inferiority or superiority study design (using within-patient comparison) may be required.

The Baha BP110 Power Sound processor on a Softband was chosen for a secondary assessment, since the ATB System mimics the performance of a Baha Power Sound Processor (with the same 55 dB fitting range) on the passive transcutaneous Baha Attract System¹. Therefore it is also a relevant choice to present as a postoperative hearing situation for the subject.

This investigation is limited to adult subjects. The paediatric population constitutes an inhomogeneous patient group (age-related), and currently there are no audiological tests that are suitable for comparisons across age ranges and across multiple countries/languages.

The follow-up period of 12 weeks post-surgery, 8 weeks post fitting for the primary analysis is chosen as it is judged as long enough for the subjects to adapt and get used to the hearing performance with this investigational device. The total length of the investigation is judged long enough to collect hearing performance and safety data as long term data.

4.3 Objectives and outcome measures

| Primary objective | Outcome measure(s) |
|--|--|
| To compare hearing performance with the Investigational device and the unaided hearing situation | At 3 months 
 • Thresholds audiometry, free-field [PTA4, Mean of 0.5, 1, 2 and 4 kHz]. Investigational |

| | |
|--|---|
| | 
device (at 3 months) vs. Unaided.
 
 Adaptive speech in noise [speech-to-noise ratio, 50% speech understanding]. Investigational Device vs. Unaided (preoperative). |
|--|---|

| Secondary objective(s) | Outcome measure(s) |
|--|---|
| 
To compare hearing performance with the Investigational device and the unaided hearing situation
 | 
 Thresholds audiometry, free-field [PTA4, Mean of 0.5, 1, 2 and 4 kHz]. Investigational Device (4w, 6 and 12 months) vs. Unaided (preoperative). Thresholds audiometry, free-field [0.25, 0.5, 0.75, 1.0, 1.5, 2.0, 3.0, 4.0, 6.0 and 8.0 kHz]. Investigational Device (4w, 3, 6 and 12 months) vs. Unaided (preoperative). Adaptive speech in noise [speech-to-noise ratio, 50% speech understanding]. Investigational Device (4w, 6 and 12 months) vs. Unaided (preoperative). Speech in quiet [% correctly perceived words at 50dB, 65dB and 80dB SPL]. Investigational Device (4w, 3, 6, and 12 months) vs. Unaided (preoperative). Feedback measurements. Investigational Device (Visit 4 and onwards). |
| 
To compare the self-reported assessments of hearing outcome with the Investigational device and in a preoperative hearing situation
 | 
 Abbreviated Profile of Hearing Aid Benefit (APHAB). Investigational Device at 3 and 12 months vs. preoperative hearing situation Health Utilities Index (HUI23S1EN.15Q) at 3 and 12 months. Investigational device vs. preoperative hearing situation. Speech, Spatial and Qualities of Hearing Scale (SSQ) at 3 and 12 months. Investigational device vs. Unaided. |
| 
To collect surgical information
 | 
 Soft tissue thickness Soft tissue reduction performed Type of anaesthesia Surgery time Bone polishing/removal at the actuator site |

| | |
|--|---|
| | 
 • BI300 Implant length • Location of BI300 Implant • Surgical incision type/location |
| To collect information about the magnet choice and daily use of sound processor | 
 • Daily usage time • Comfort • Softpad use • Choice of magnet strength |
| To measure hearing performance preoperatively with a Baha BP110 Power sound processor on a Baha Softband | 
 • Thresholds audiometry, free-field [PTA4, Mean of 0.5, 1, 2 and 4 kHz]. • Thresholds audiometry, free-field [0.25, 0.5, 0.75, 1.0, 1.5, 2.0, 3.0, 4.0, 6.0 and 8.0 kHz]. • Speech in quiet [% correctly perceived words at 50dB, 65dB and 80dB SPL]. • Adaptive speech in noise [speech-to-noise ratio, 50% speech understanding]. • BC Direct [0.25, 0.5, 0.75, 1.0, 1.5, 2.0, 3.0, 4.0 and 6.0 kHz]. |
| Tertiary Objective | Outcome measure(s) |
| To measure hearing performance preoperatively with a current hearing aid (if used by the patient). | 
 • Adaptive speech in noise [speech-to-noise ratio, 50% speech understanding]. |

| Safety objective(s) | Outcome measure(s) |
|---|---|
| Primary safety analysis at 6 months. | |
| Implant site evaluations | Numbness |
| Adverse Events and concomitant medication/treatment | Information will be collected from Visit 2 and onwards. |
| Device deficiency | Information will be collected from Visit 2 and onwards. |
| Audiogram | Bone conduction thresholds preoperative and postoperative (3, 6, and 12 months) |

4.3.1 Demographics and baseline variables

Demographics and baseline variables to be collected during visit 1 are the following:

- Demographics

- Medical history
- Baseline characteristics
- Audiogram
- Eligibility criteria (inclusion/exclusion criteria)
- Informed consent

5 PROCEDURES

Procedures that will be performed during the clinical investigation is outlined in the flow chart, see section 6.

5.1 Test equipment

The test set-up regarding speaker placement, sound room facility and software used at each clinic shall be checked and approved by the Sponsor at the latest during the Site initiation visit. All tests shall be performed in the sound isolated room. Equipment used for audiological testing shall be calibrated before initiation of the investigation. Calibration certificates will be asked for by the Sponsor as part of the study documentation. It is important to keep the same sound room and test equipment set-up during the entire clinical investigation. Changes are not allowed.

If, for some exceptional reason, any significant changes would be needed with the test equipment during the investigation a new calibration needs to be performed together with a new unaided baseline measurement. Calibration documentation should be kept with the Investigator File.

5.2 Demographics

The following demographic data will be recorded at Visit 1:

- Age collected as date of birth (month and year)
- Gender
- Ethnicity
- Nicotine use (Subjects does not smoke, ≤ 10 cigarettes/day, 11-20 cigarettes/day, 21-40 cigarettes/day, > 40 cigarettes/day)

5.3 Medical history

The following information will be recorded at Visit 1:

- Relevant medical and surgical treatment during the past three years judged by the investigator
- Current concomitant medication and treatments

5.4 Baseline characteristics

During visit 1 a number of baseline characteristics will be recorded;

- Treatment ear (indicate left or right or both. In case of both, indicate side for hearing tests)
- Type of hearing loss: (Conductive, Mixed or SSD)
- Aetiology: (chronic) infection, tumour, trauma, malfunction, otosclerosis, other

- Current hearing aid (yes/no, specify model, side and years of hearing aid use, reason for change)
- Previous experience from amplified sound through properly fitted amplification (yes/no, specify type, years of aid in use, when stopped use, reasons stop using)
- Has the subject previously been suggested a bone conduction hearing implant (BCHI) solution (yes/no, reason for rejection)

5.5 Audiogram

Unaided audiometric threshold measures (including both air- and bone conduction thresholds) should demonstrate that the subject has a conductive, mixed hearing loss or single-sided sensorineural deafness and meets the audiological inclusion criteria.

An existing audiogram may be used as long as it has been completed during the last six months, and contains all the required relevant frequencies (250, 500, 750, 1000, 1500, 2000, 3000, 4000, 6000 and 8000Hz). The subject's pre-operative Pure Tone Average PTA4 (mean of 500, 1000, 2000 and 4000Hz) should be computed and recorded to ensure the subject meets the inclusion criteria.

If an audiogram is older than 6 months or does not contain the required frequencies, a new will be performed at Visit 1. Frequencies required for air conduction thresholds are 250, 500, 750, 1000, 1500, 2000, 3000, 4000, 6000 and 8000Hz. Bone conduction thresholds are 250, 500, 750, 1000, 1500, 2000, 3000, 4000 and 6000Hz. Contralateral masking should be used if needed, and according to local practice. The hearing care professional shall always record the unmasked threshold and record the masked if applicable.

Audiograms for bone conduction thresholds will also be performed at Visits 6, 7, and visit 8 to monitor hearing thresholds postoperatively.

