7.2.4 Clinically significant threshold shifts

Shifts in threshold, relative to the preoperative baseline, will be reported as an adverse event (AE) when a shift at any frequency exceeds 15 dB HL.

7.2.5 Handling and reporting of AESIs, SAEs and device deficiency that could have led to a SAE

An investigator should report within 24 hours, after being aware of the event, an AESI, SAE or a device deficiency that could have led to a SAE. The report shall be sent as an email attachment to the safety inbox or faxed to Cochlear Bone Anchored Solutions AB. Contact information is available on the SAE form.

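### The preoperative bone-conduction baseline for the threshold-shift adverse event rule may be an audiogram up to six months old, and the protocol does not say whether it must come from the study set-up

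*Protocol*

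**What the plan says.** Protocol 5.5 gives the preoperative audiogram the task of showing the type of hearing loss and that the subject "meets the audiological inclusion criteria". It then allows a substitute: "An existing audiogram may be used as long as it has been completed during the last six months". The second condition concerns coverage; the substitute qualifies only if it "contains all the required relevant frequencies (250, 500, 750, 1000, 1500, 2000, 3000, 4000, 6000 and 8000Hz". A new test is needed only when one of these two conditions fails: "If an audiogram is older than 6 months or does not contain the required frequencies, a new will be performed at Visit 1".

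Protocol 4.3 names the audiogram as a safety outcome: "Bone conduction thresholds preoperative and postoperative (3, 6, and 12 months" are the time points. Protocol 7.2.4 ties adverse event reporting to it: a shift, "relative to the preoperative baseline, will be reported as an adverse event (AE) when a shift at any frequency exceeds 15 dB HL".

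Protocol 5.1 requires testing in the sound isolated room and calibration before the investigation starts. It adds: "It is important to keep the same sound room and test equipment set-up during the entire clinical investigation. Changes are not allowed". If a significant equipment change is unavoidable, it asks for recalibration and a new unaided baseline.

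SAP 3.3.4 describes the baseline as the Visit 1 audiogram, and SAP 4.11.4 presents audiograms by visit. Neither mentions an earlier test date or an outside source.

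**The concern.** An audiogram some months old is reasonable evidence for eligibility. It is a weaker reference for a within-subject safety comparison, where whatever separates it from the subject's true threshold at Visit 1 carries straight into the postoperative shift. The aetiologies recorded under Protocol 5.4 include chronic infection, tumour and otosclerosis, so some thresholds may move without surgery. A different room or audiometer adds a further offset. There is no control group in which to see such changes.

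Two errors are possible. If the old audiogram shows better thresholds than the subject had at Visit 1, an event may be reported with no loss after Visit 1. If it shows worse ones, a true postoperative loss may stay below the limit. The second matters more for safety, because it leaves no trace in the adverse event tables.

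**Working it through.** **Comparison of the texts**

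1. Protocol 5.5 sets two acceptance conditions, age and frequency coverage. It states none on site, room, audiometer or calibration and does not refer to 5.1.
2. The flow chart (Protocol 8) schedules one preoperative audiogram. The only other preoperative bone-conduction record is BC Direct (Protocol 5.11), which is unmasked and measured through the reference processor on a Softband. The accepted audiogram is therefore the baseline meant in 7.2.4.
3. Protocol 5.1 governs testing during the investigation and does not say whether it reaches back to an audiogram made before Visit 1. This is a gap between 5.1 and 5.5.
4. The primary endpoints use the unaided free-field thresholds and unaided speech in noise, both measured at Visit 1 (Protocol 6.2 and 6.4). They do not depend on this audiogram.
5. The six-month limit is most naturally counted back from Visit 1. The flow chart gives no window between Visit 1 and surgery, so the audiogram can be more than six months old at surgery.

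**Illustration of size**

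The plan states no figure on this point to reproduce. From the documents: 9 bone-conduction frequencies (Protocol 6.1), a limit of more than 15 dB at any one of them (7.2.4), and 50 subjects (Protocol 10.3.3). Assumed, because the documents are silent: SD *s* of the test-retest change at one frequency, 5 to 7 dB; offset *m* between the old audiogram and the true Visit 1 threshold, 0, 5 or 10 dB; no true change after Visit 1; one postoperative visit.

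For one frequency, p = 1 − Φ((15 − m)/s). For at least one of nine independent frequencies, P = 1 − (1 − p)^9.

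| s | m | p | P | 50 × P |
|---|---|---|---|---|
| 5 | 0 | 0.0013 | 1.2% | 0.6 |
| 5 | 5 | 0.0228 | 18.7% | 9.4 |
| 5 | 10 | 0.1587 | 78.9% | 39.4 |
| 7 | 0 | 0.0161 | 13.6% | 6.8 |
| 7 | 5 | 0.0766 | 51.2% | 25.6 |
| 7 | 10 | 0.2375 | 91.3% | 45.6 |

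Sensitivity to the model, with ranges running from s = 5 to s = 7:

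| Model | m = 0 | m = 5 | m = 10 |
|---|---|---|---|
| Between-frequency correlation 0.8 | 0.7%-5.7% | 7.8%-20.5% | 35.9%-47.8% |
| Independent, 5 dB recording steps (limit met at 20 dB or more; cut at 17.5) | 0.2%-5.5% | 5.5%-28.8% | 46.3%-74.8% |

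The last column of the first table supposes that all 50 subjects bring an old audiogram with that offset. If only a share *f* do, the extra events number 50 × f × (P at m − P at 0). For s = 5, m = 5 and an assumed f = 0.2, this is 50 × 0.2 × (0.187 − 0.012) = 1.75. The documents do not give f.

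A second simulation used 5 dB steps, the 3- and 6-month visits together, a random set-up offset per subject (SD 3 to 5 dB) and 0 to 3 dB drift. Single-test SDs of 3.5 and 5 dB correspond to s of about 5 and 7 (multiply by √2). With a same-set-up baseline, 0.6% and 12.1% met the rule. With offset and drift, 2.6%-17.5% and 17.0%-38.5% did. If all 50 subjects used old audiograms, that is 50 × (0.026 − 0.006) = 1 to 50 × (0.385 − 0.121) = 13 extra events.

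**Masking**

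Suppose a true 20 dB loss at one frequency and an old audiogram that reads k dB too poor. The chance of exceeding the limit at that frequency is Φ((20 − k − 15)/s). This is 84% (s = 5) or 76% (s = 7) at k = 0, 50% at k = 5, and 16% or 24% at k = 10.

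**The case against.** The strongest case against has five parts.

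- **No text permits outside equipment.** This is right. A reader might infer that the protocol accepts a baseline from any equipment, but that reads a permission into silence. Protocol 5.1 demands calibrated equipment and an unchanged set-up, and could be taken to cover the existing audiogram. What stands is that nothing says so, and a site reading 5.5 alone would find no bar.
- **A shift is not automatically a device effect.** A reader might infer that every preoperative change is counted against the device. Only shifts above 15 dB are events, the investigator assesses relationship to the device (Protocol 7.2.2), and the SAP counts an adverse device effect only when an event is rated probably related to device or procedure (SAP 3.3.2). The event still enters the all-event tables (SAP 4.11.2), and the investigator may have no preoperative audiogram from the study set-up to judge it against.
- **The consequence is limited.** A threshold shift is not in itself an event of special interest (Protocol 7.2.3). The SAP plans no test or count of shifts and presents audiograms at Visits 1, 6 and 8 only. A reader might infer that the 6-month primary safety analysis is compromised as a whole. The documents do not support that: no 6-month audiogram presentation is planned in the SAP, so the route into that analysis is the adverse event count.
- **BC Direct gives a Visit 1 record at the same nine frequencies.** It helps as a plausibility check but cannot replace an audiogram.
- **The figures rest on assumptions, and the rule is noisy anyway.** This stands. With s = 7, 13.6% of subjects meet the rule with no offset at all, and the upper end of the second simulation comes largely from the assumed drift. Correlation between frequencies lowers all the figures.

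**Conclusion.** The point holds as a gap in the plan. An audiogram accepted for eligibility also becomes the safety baseline, with an age allowance of six months and no stated set-up condition. It can produce a spurious threshold-shift adverse event or hide a real one. The effect is confined to those events and to a descriptive safety variable; the primary efficacy endpoints are untouched.

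The direction of the effect follows from the text. Its size does not: it depends on the test-retest SD, the set-up offset, the drift and the share of subjects who bring an old audiogram, none of which the documents give. The figures above show only that a modest offset matters against a limit applied to any of nine frequencies. They are not a forecast of event counts.

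A Visit 1 baseline would remove drift before Visit 1 and set-up differences. It would not remove disease course after Visit 1, including the unrestricted interval to surgery, nor the noise of the any-frequency rule. This is an inexpensive improvement to the safety record, not a defect that undermines the trial's main conclusions.

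**What to change.** In Protocol 5.5, restrict the existing audiogram to eligibility. State that the bone-conduction thresholds used as baseline for 7.2.4 and for the audiogram tables are measured at Visit 1 on the calibrated study set-up described in 5.1.

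For subjects already enrolled with an older audiogram, record its date and source. In the SAP, tabulate shifts above 15 dB with and without these subjects.

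The cost is a one-sentence amendment, a short SAP addition, and a little more test time at Visit 1 for subjects who bring an existing audiogram. Visit 1 already includes a scheduled audiogram and other hearing tests, so no extra visit is needed.
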